3.2.2 Power for analysis of selected secondary variables

The following test of secondary variables are part of the global testing strategy.

For the paired differences of numbers of NSVT, SVT, ICD shocks and ATP over ACEI/ARB and ARNI treatment period, the above sample size will provide >95% power to detect mean of paired difference of at least -3 and standard deviation of at most 10. These are under the assumption of similar patient experiences as de Diego et al (2018)'s study.

For the change from date of treatment initiation after 6 months of treatment assessed by LVEF and NT-proBNP, the above sample size will provide 84% - 91% power to detect a treatment difference of 3 numeric values at the two-sided significance level of 0.05, assuming a standard deviation of 15.

3.3 Dose escalation and dose modification

Investigational or other study treatment dose adjustments and/or interruptions are under investigator's discretion and according to product labels. Up-titration of patient's drug should

be according to the target dose or to the patient's maximum tolerance level.

3.3.1 Dose escalation guidelines

The dosage of ACEI/ARB and ARNI are under Investigator's discretion according to the recommended dosage (Yancy et al 2017) (Table 3-1). The recommended starting dose of ARNI for different population is presented in Table 3-2. If the patient is well tolerated, the dose of study drug should be up-titrated to next dose level until to target dose. Down-titration of the study drug at any time based on the judgment of the Investigator will be allowed with the consideration for patient safety and tolerability.

Compound	Initial dose	Target dosage
ARNI (Sacubitril/Valsartan)	50 – 100 mg bid	200 mg bid
ACEI		
Enalapril	2.50 mg bid	10 mg bid
Captopril	6.25 mg tid	50 mg tid
Perindopril	2.00 mg qd	8 mg qd
Ramipril	1.25 mg qd	10 mg qd
Benazepril	2.5 mg qd	20 mg qd
ARB		
Candesartan	4 mg qd	32 mg qd
Valsartan	40 mg bid	160 mg bid
Losartan	25 – 50 mg qd	150 mg qd

Table 3-1 Recommended dosage

Table 3-2 Recommended	starting dose of ARNI
1 abic 5-2 itecommended	

Population	Initial dose
Moderate or high-dose ACEI (equivalent of enalapril ≥ 10 mg bid)	100 mg bid
Moderate or high-dose ARB (equivalent of valsartan ≥ 80 mg bid)	100 mg bid
Low dose ACEI (equivalent of enalapril < 10 mg bid)	50 mg bid
Low dose ARB (equivalent of valsartan < 80 mg bid)	50 mg bid
Severe renal impairment (eGFR < 30 mL/min/1.73 m ²)	50 mg bid
Moderate hepatic impairment (Child-Pugh Class B)	50 mg bid
Elderly (age \geq 75 years)	50 mg bid

3.3.2 Definitions of dose limiting toxicities

A dose limiting toxicity (DLT) is defined as an adverse event or abnormal laboratory value assessed as unrelated to disease, disease progression, inter-current illness, or concomitant medications that occurs when taking study drugs. Dosage of study drugs is according to product label. Patients who meet any of the DLTs defined in the product label will be withdrawn from this study.

3.3.3 Dose modifications

Dose modifications are according to investigator's discretions and follow the local product label.

3.4 Interim analyses

The interim analysis (IA) and endpoint analysis will be performed in this study. An interim analysis will be performed when half of the required sample size (110 patients) have completed the 12-month treatment and follow-up period or prematurely withdrawn from study after at least one ARNI treatment, aiming at analyzing the study endpoints and safety, as well as re-evaluating the minimum sample size required.

For this interim analysis, the efficacy analysis will include efficacy data from 117 eligible subjects (i.e., subjects who have used ARNI at least once before freezing of the interim analysis data and completed the trial or early withdrawn).

Other analyses include all data from these 117 subjects and all subjects enrolled before these subjects.

4. Study Endpoints

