Study treatment discontinuation	When the patient permanently stops taking any of the study drug(s) prior to the defined study treatment completion date (if any) for any reason; may or may not also be the point/time of study discontinuation.	
Treatment arm/group	A treatment arm/group defines the dose and regimen or the combination, and may consist of 1 or more cohorts.	
Variable (or endpoint)	The variable (or endpoint) to be obtained for each patient that is required to address the clinical question. The specification of the variable might include whether the patient experiences an intercurrent event.	
Withdrawal of consent	Withdrawal of consent from the study occurs when the participant explicitly requests to stop use of their data and/or biological samples AND no longer wishes to receive study treatment, AND does not agree to further protocol required assessments. This request should be in writing (depending on local regulations) and recorded in the source documentation.	
	This request should be distinguished from a request to discontinue the study. Other study participant's privacy rights are described in the corresponding informed consent form.	

Amendment 2 (Feb 2022)

Amendment rationale

Study was initiated in 19-Oct-2020. As of 31-Jan-2022, a total of 142 patients have been enrolled in the study. The slow enrollment of patients was impacted by the COVID-19 pandemic. This amendment is aimed to reduce the study sample size by modification of the statistical power of sample size calculation.

Changes in the protocol

Chapter	V01	V02	Reason
Protocol summary (Study design), Section 3, Section 5	275 HFrEF patients	219 HFrEF patients	Sample size is updated
Protocol summary – Exclusion criteria	2. Patients who received ARNI within 6 weeks prior to study	2. Patient received target dose (≥200 mg/d) of ARNI for 2 weeks continuously within the 6-week period prior to study enrollment.	Define 6-week period

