4.5 Purpose and timing of interim analyses/design adaptations

The study will have one interim analysis (IA) and one final analysis (FA). The intent of the interim analysis is to stop for futility or high incidence of safety events and re-evaluate minimum sample size required. It is planned once at least 110 patients (half of the required sample size) have completed the study. All study endpoints stated in Section 2 will be analyzed.

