8.5 External central review committee

A central review committee is responsible for periodic study endpoint events adjudication and SAE review in Rhythm Study. The central review committee is an independent group consisting of individuals who have experience and expertise in the management of trial participants within heart failure area and in the monitoring of ICD/CRT-D device. The review committee will be separated to two subgroups to perform device data adjudication and SAE review respectively.

Device data report will be exported timely into PDF version by doctors at baseline, 1 month, 3 months, 6 months, 9 months, 12 months when patient visits happen in local sites and all uncertain device events will be sent to the subgroup 1 for adjudication (Device Data adjudication Boards).

All aggregated SAE data will be provided to the subgroup 2 for review (Data and Safety Monitoring Boards, DSMB).

Then committee will have a meeting held by chairman either in the site or by conference call when necessary. Central review committee members will make every attempt to attend the meeting in person or by conference call. Total central review committee members will review and interpret device data (include VA events, ICD-shock, ATP, etc) and aggregated SAE data.

The central review committee members vote on all decisions. The member must be present in the meetings or must have given written recommendation to the chair prior to the meeting. Voting is by voice vote, but any members may request a secret written ballot. After decision making, the Chairman will provide minutes of the Board discussions to all Board members provide a summary (executive) report of each Board meeting to Novartis. A summary statement and recommendation from chairman will be provided in writing to the Novartis Medical Responsible within three working days of each meeting. The recipients will acknowledge receipt and provide a response, if necessary. If an urgent report (defines according to investigator discretion) is needed to interpret, at least 3 committee members should response and give their consensus decision to the investigator.

Committee Responsibility:

1. Endpoints adjudication use for final study

- 2. Provide clinical suggestion to investigators
- 3. Make amendment for protocol to NVS, for example patient exclusion and enrollment criteria

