10.2 Additional safety monitoring

An external central review committee for this study will also periodically review aggregated SAE data, and make recommendation to sponsor if needed, e.g., protocol amendment on inclusion/exclusion criteria. See Section 8.5 in the protocol for details of the external central review committee.

11 Data collection and database management

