4.4 Past and concomitant medication and concurrent treatment

The CRF collects the drug name, total daily dose and unit, frequency of administration, route of administration, start date, end date, ongoing or not, and indication for prior and concomitant medications.

The CRF collects the name, start date, end date, ongoing or not, and indication of concomitant treatments (non-drug concomitant treatments, including surgery).

4.5 **Protocol Deviation and Medication Compliance**

Protocol deviations will be recorded by the clinical monitor.

Medication compliance for ACEI/ARB and ARNI is defined as: total actual dose/total planned dose *100%. Overall medication compliance for ACEI/ARB and ARNI will be summarized.

5. Statistical Hypotheses

For details, see section 7.4 Efficacy Analysis.

6. Analysis Datasets

The analysis data sets of this study are as follows.

Screened set

It includes all subjects who have signed the informed consent form.

Safety Analysis Set, SS

It includes all subjects who had received at least one dose of study treatment. Analyses will be performed according to the study treatment received. The safety analysis set will be used for all analyses except the efficacy analysis.

Efficacy Analysis Set

It includes SS subjects who have received ARNI at least once and completed 12 months of complete treatment and follow-up or who have early withdrawn from the study after receiving ARNI at least once. The efficacy analysis set will be used as the primary population to analyze the efficacy variables.

Per Protocol Set, PPS

It includes subjects in efficacy analysis set who had no major protocol violations, and the PP population will be used for efficacy analysis.

7. Statistical Methods

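### SAP 3.4 leaves treated subjects enrolled after the last of the 117 out of the interim safety tables, although protocol 4.5 lets the interim stop the trial for safety

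*SAP*

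**What the plan says.** Protocol 4.5 states the purpose: "The intent of the interim analysis is to stop for futility or high incidence of safety events and re-evaluate minimum sample size required".

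SAP 3.4 sets the trigger: "when half of the required sample size (110 patients) have completed the 12-month treatment and follow-up period", or have withdrawn early after at least one ARNI dose. It then fixes the data. For efficacy, "the efficacy analysis will include efficacy data from 117 eligible subjects", meaning subjects with at least one ARNI dose who completed or withdrew before the freeze. For the rest: "Other analyses include all data from these 117 subjects and all subjects enrolled before these subjects". Its stated aims are to analyse the endpoints and safety and to revisit the sample size; stopping is not mentioned.

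SAP Section 6 defines the Safety Analysis Set as all subjects with at least one dose of study treatment and adds: "The safety analysis set will be used for all analyses except the efficacy analysis".

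On the committee, protocol 10.2 says it "will also periodically review aggregated SAE data", and 8.5 also opens by calling the review periodic. The sentence in 8.5 on meetings reads: "Then committee will have a meeting held by chairman either in the site or by conference call when necessary".

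**The concern.** Restricting efficacy to subjects who have reached ARNI and then finished or left suits a paired comparison. Safety does not need that restriction: a subject who has taken one dose contributes exposure and adverse events, whether or not the second period is over. Carrying the enrolment cut into the safety tables discards recorded data on patients under treatment, and neither document gives a reason.

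At stake is the incidence on which any safety recommendation at the interim would rest. The omitted patients are the later enrolees. They are also the ones a stop could still protect, because they are either in their ARNI period or have yet to start it.

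**Working it through.** **The plan's own figures.** 175 / (1 − 0.20) = 218.75, so 219. 219 / 2 = 109.5, so 110. Both agree with the plan. The efficacy count of 117 is taken from SAP 3.4.

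**Accrual.** The rationale for protocol Amendment 2 gives a start on 19-Oct-2020 and says: "As of 31-Jan-2022, a total of 142 patients have been enrolled in the study". That is 469 days. 469 / 30.4375 = 15.41 months, and 142 / 15.41 = 9.22 per month. At that rate 219 is reached at 219 / 9.22 = 23.8 months.

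**Simplest case: no dropout, constant accrual.** The 117 are the first 117 enrolled.
- Cut-off: 117 / 9.22 + 12 = 24.7 months, when all 219 are enrolled.
- Left out: 219 − 117 = 102 (46.6%).
- Past Month 6 by then (enrolled by month 18.7): 18.7 × 9.22 = 172, of whom 172 − 117 = 55 are left out.
- Omitted share of ARNI-exposed subjects: 55 / 172 = 32%. The other 102 − 55 = 47 are still on ACEI/ARB.

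**Same case, accrual halved after January 2022 (4.61 per month).**
- Enrolled at 24.7 months: 142 + 9.29 × 4.61 = about 184; left out: about 67.
- Past Month 6: 142 + 3.29 × 4.61 = about 157; ARNI-exposed left out: 40 / 157 = 25%.

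**With dropout.** The 117 include anyone who withdrew after an ARNI dose, however late they enrolled. I simulated this with dropout spread evenly over 12 months, the cut-off at the 117th qualifying subject, and coverage of everyone enrolled up to the last of the 117. The plan's own dropout allowance is 20%. Figures are averages, and enrolled subjects are taken as dosed.

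| Accrual after Jan 2022 | Dropout | Enrolled at cut-off | Left out | ARNI-exposed left out |
|---|---|---|---|---|
| Unchanged | 0% | 219 | 102 (47%) | 55 of 172 (32%) |
| Unchanged | 10% | 219 | 79 (36%) | 35 of 168 (21%) |
| Unchanged | 20% | 219 | 64 (29%) | 24 of 164 (15%) |
| Halved | 0% | 184 | 67 (36%) | 40 of 157 (25%) |
| Halved | 10% | 187 | 53 (28%) | 24 of 151 (16%) |
| Halved | 20% | 190 | 46 (24%) | 17 of 146 (12%) |

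**Wording.** The phrase about subjects enrolled before the 117 could mean before the first or before the last of them. Whoever enrolled after the last is outside on either reading. On the before-the-first reading, late enrolees who withdrew on ARNI count while comparable ongoing patients do not, which would distort the incidence.

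**What it does to detection.** The chance of seeing at least one case of an event with a 1% risk is 1 − 0.99ⁿ. Among ARNI-exposed subjects:
- No dropout: n = 117 gives 69%; n = 172 gives 82%.
- 20% dropout: n = 164 − 24 = 140 gives 76%; n = 164 gives 81%.

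These gains are upper limits, because late enrolees have shorter ARNI exposure.

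**The case against.** The strongest reply is that the safety of later enrolees does not depend on these tables. Protocol 10.1.3 sends every SAE to the sponsor within 24 hours. Protocol 8.5 sends all aggregated SAE data to subgroup 2, labelled the DSMB, without limiting it to the 117, and provides for urgent consultation. Protocol 9.2.2 lets the sponsor terminate at any time for an unacceptable safety risk. All of this stands. A reader might infer that nothing ensures a safety review outside the interim; the documents do not support that. Individual reports do not, however, supply an incidence by treatment period, and that is what a stop for high incidence would use.

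A second reply is that the 117 are not simply the earliest enrolees. Late withdrawals on ARNI count among them, and those are the most safety-relevant cases. This also stands, and it is why the share falls in the dropout rows. A reader might infer that a third to a half of exposed patients are omitted. For ARNI exposure about a third is the ceiling, reached only with no dropout.

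Third, a specific interim rule may override a general set definition, and a cohort cut eases data cleaning before a freeze. That is a possible motive, but the SAP does not state it.

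Two further inferences go too far. One is that the committee text contradicts itself: data can be reviewed periodically and meetings called as needed, so what is missing is a stated interval. The other is that the interim comes too late to protect anyone. Its timing follows from the 12-month paired design, and in the simplest case 47 patients have not yet started ARNI and 55 are in their ARNI period.

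**Conclusion.** The point holds for the interim data rule. SAP 3.4 takes the safety tables from a narrower set than SAP Section 6 prescribes, while protocol 4.5 gives those tables a stopping role. About 46 to 102 enrolled subjects would be left out, and about 12% to 32% of those exposed to ARNI.

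The range rests on accrual staying at 9.2 per month or halving after January 2022, on dropout of 0% to 20%, and on the before-the-last reading of the cut. The sponsor can replace it with a count from the enrolment log. The early accrual rate is itself uncertain, since the protocol attributes slow enrolment to the pandemic.

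This is a defect in what the interim can show about incidence, not an absence of safety oversight. It should be corrected because the correction is simple and the omitted data are already being collected. The committee's meeting interval is a secondary clarification.

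**What to change.** - **SAP 3.4, data:** run the interim safety analyses on every subject in the Safety Analysis Set, with all data up to the cut-off date, by treatment period and with exposure time. Keep the 117-subject restriction for efficacy only.
- **SAP 3.4, aim:** bring it into line with protocol 4.5, so that both documents say whether the interim can stop the trial for safety.
- **Protocol 8.5 and 10.2, secondary:** reconcile the periodic review with the as-needed meetings by stating an interval, and say that subgroup 2 receives the interim safety tables.

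The cost is a few sentences, using a committee and a data flow that already exist. The drawback is that later enrolees' data will be less clean at the cut-off and their exposure shorter, which is why rates should be shown against exposure time.

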4.1 Efficacy Endpoints

4.1.1 Primary endpoints

• Assessment of ventricular arrhythmia events

The proportion of subjects with VA events over 6 months of ACEI/ARB and 6 months of ARNI treatment will be statistically summarized.

Cardiac arrhythmia of \geq 3 consecutive complexes originating in the ventricles at a rate > 100 bpm (cycle length: < 600 ms). Ventricular arrhythmia events that will be measured through device to determine SVT, NSVT and PVC:

- 1. Sustained ventricular tachycardia (SVT) is defined as tachycardia lasting for \geq 30 seconds or with hemodynamic disorder as determined by Holter and/or device.
- 2. Non-sustained ventricular tachycardia (NSVT) is defined as recorded by Holter and/or device
- 3. Premature ventricular contraction (PVC) is defined as an early ventricular depolarization as determined by the device, and/or detected by Holter
- Assessment of anti-tachycardia pacing and implantable cardioverter-defibrillator shocks

The proportion of subjects with ATP, ICD, or CRT-D shocks over 6 months of ACEI/ARB and 6 months of ARNI treatment will be statistically summarized.

Once VA are detected, ICD can treat with high-energy shocks or ATP. ATP consists of one or more trains of pacing stimuli, expressed as a percentage of the tachycardia cycle length for a given RR interval, from the onset of the preceding R wave.

Subjects with sustained VA events will receive ICD or CRT-D shock therapy. Inappropriate shocks may occur in subjects with atrial fibrillation, SVT, or other intracardiac or extra cardiac signals. An inappropriate shock is defined as a shock not delivered for VT or VF and ending if sinus rhythm is redetected by the ICD. If a subsequent episode started within 5 minutes after the previous episode ended, it will be not considered as a new episode (van Rees et al 2011).

4.1.2 Secondary endpoints

• Number of occurrences of VA

The episodes of VA events over 6 months of ACEI/ARB and 6 months of ARNI treatment will be measured.

• Left ventricular ejection fraction

Left ventricular ejection fraction (%) will be compared at baseline, Month 6 and EOS.

• NYHA level

NYHA level will be recorded by investigators and compared at baseline, Month 6 and EOS.

• NT-proBNP

The measurements of NT-proBNP will be obtained from serum and plasma. Samples will be obtained before patients take their morning study drug dose. NT-proBNP (pg/mL) will be compared between ACEI/ARB and ARNI treatments at baseline, Month 6 and EOS.

• Number of hospitalizations

Number of hospitalizations for arrhythmia or HF related hospitalizations will be recorded during ACEI/ARB and ARNI treatments.

4.2 Safety Endpoints

4.2.1 Duration of exposure and exposure dose

In this study, detailed information such as date, time, dose and frequency of administration will be recorded in the CRF. The extent of exposure to ACEI/ARB and ARNI will be investigated, and the duration of exposure and planned and actual doses will be calculated.

Duration of exposure (days) = date of the last dose of the IMP - date of the first dose of the IMP + 1 If the subject's duration of drug exposure is discontinuous, the number of days without drug use will not be counted.

Total planned dose (mg) = total planned daily dose recorded in CRF * duration of exposure (days). Total actual dose (mg) = total actual daily dose recorded in CRF * duration of exposure (days).

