6.6 Additional treatment guidance

6.6.1 Treatment compliance

The investigator must promote compliance by instructing the patient to take the study treatment exactly as prescribed and by stating that compliance is necessary for the patient's safety and the validity of the study. The patient must also be instructed to contact the investigator if he/she is unable for any reason to take the study treatment as prescribed. Compliance will be assessed by the investigator and/or study personnel at each visit using drug tablet counts and information provided by the patient or guardian via a self-administered diary card. Compliance should be ensured by the investigator to be > 80%. This information should be captured in the source document at each visit. All study treatment dispensed and returned must be recorded in the Drug Accountability Log.

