7.3.6 Treatment compliance

The analysis is performed based on the SS.

The study drug compliance will be described statistically as a quantitative variable.

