7.5 Safety Analysis

7.5.1 Drug exposure

The analysis is performed based on the SS.

The exposure to the study drug (duration of exposure, total planned dose, total actual dose) will be statistically described and summarized by treatment group and by mean, standard deviation, median, minimum, and maximum.

The number and percentage of patients in each treatment group will be summarized for duration of exposure in the following groups.

- < 30 days
- 30 days <= duration of exposure <60 days
- 60 days <= duration of exposure <90 days
- 90 days <= duration of exposure <120 days
- 120 days <= duration of exposure <150 days
- 150 days <= duration of exposure <180 days
- Duration of exposure >=180 days

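### SAP compliance does not measure whole missed days, because planned and actual dose are multiplied by the same days on drug, so it cannot be read against the protocol's target of more than 80%

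*SAP*

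**What the plan says.** SAP 4.2.1 defines duration of exposure as last dose date minus first dose date plus one, and then removes gaps: "If the subject's duration of drug exposure is discontinuous, the number of days without drug use will not be counted". Two totals are built on that duration. The planned one reads: "Total planned dose (mg) = total planned daily dose recorded in CRF * duration of exposure (days"). The one for drug taken has the same form and the same multiplier, with the actual daily dose in place of the planned.

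SAP 4.5 takes their ratio: "Medication compliance for ACEI/ARB and ARNI is defined as: total actual dose/total planned dose *100"%. It adds: "Overall medication compliance for ACEI/ARB and ARNI will be summarized". SAP 7.3.6 specifies the output: "The study drug compliance will be described statistically as a quantitative variable". No count against a threshold is planned.

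Protocol 6.6.1 uses the same word for something else. Compliance there is judged at each visit from tablet counts and a diary card, with a stated target: "Compliance should be ensured by the investigator to be > 80"%. That section places the information in the source document. Protocol Table 8-1 also marks diary card collection and a compliance assessment at Visits 2 to 7, and its footnote says that marked items go into the clinical database or arrive electronically from a vendor.

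**The concern.** A compliance figure should fall when a patient goes without drug for days at a time. Here the numerator and the denominator carry the same number of days, so a gap drops out of both. The figure that remains compares the recorded daily dose with the planned daily dose on dosing days.

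The study compares two consecutive open-label periods in the same patients. ARNI is supplied by the sponsor and reconciled at visits; ACEI/ARB is prescribed under routine care. The primary estimand ignores treatment discontinuation and dose changes, so a reader will want to know how much drug was taken in each period. A reader who meets a figure labelled compliance will naturally set it beside the protocol's target of more than 80%. The SAP ratio cannot support that comparison.

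**Working it through.** **Inputs**

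- Formulas for duration, planned dose and actual dose: SAP 4.2.1. Compliance ratio: SAP 4.5.
- Target of more than 80%: Protocol 6.6.1.
- Planned length of each period, 6 months: Protocol 6.1.5. I assume 180 days.
- Visit windows, Protocol Table 8-1: Month 6 and Month 12 each ±2 weeks. The ACEI/ARB period then runs 166 to 194 days (180 ± 14) and the ARNI period 152 to 208 days (180 ± 28).
- Longest single gap before study treatment must be discontinued: 14 days (Protocol 9.1.1).
- Assumption: the CRF actual daily dose is the dose on days taken.

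The plan states no compliance result, so there is no figure to reproduce.

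**Step 1: the SAP ratio.** Let D be days on drug.

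Compliance = (actual daily dose × D) / (planned daily dose × D) = actual daily dose / planned daily dose.

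D cancels. It would also cancel if off-drug days were counted in both totals, so the cause is the shared multiplier and not only the sentence that removes gaps.

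**Step 2: full planned dose on dosing days, period of L = 180 days.** Days covered = (L − days off) / L.

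| Days off drug | Days covered | SAP compliance |
|---|---|---|
| 14 (one gap) | 166/180 = 92.2% | 100% |
| 28 (two gaps) | 152/180 = 84.4% | 100% |
| 36 | 144/180 = 80.0%, not above 80% | 100% |
| 42 (three gaps) | 138/180 = 76.7% | 100% |

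**Step 3: visit windows, 42 days off.**

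- ACEI/ARB: 124/166 = 74.7% to 152/194 = 78.4%.
- ARNI: 110/152 = 72.4% to 166/208 = 79.8%.

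All lie below 80%, and SAP compliance is 100% throughout. The first number of days off that misses the target is 31, 34, 39 and 42 for L = 152, 166, 194 and 208.

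**Step 4: titration with planned dose taken.** Take 100 mg/day for 60 days with 14 off, then 200 mg/day for 120 days with 28 off.

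- SAP: (46 × 100 + 92 × 200) / (46 × 100 + 92 × 200) = 23,000/23,000 = 100%.
- Calendar days: 23,000 / (60 × 100 + 120 × 200) = 23,000/30,000 = 76.7%.

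**Step 5: one segment taken below plan.** Take 90 days at 200 of 400 mg planned, then 90 days at 400 of 400 mg.

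- No gap: (18,000 + 36,000) / (36,000 + 36,000) = 75.0%.
- 28 days missed in the second segment: (18,000 + 24,800) / (36,000 + 24,800) = 42,800/60,800 = 70.4%.
- The same 28 days missed in the first segment: (12,400 + 36,000) / (24,800 + 36,000) = 48,400/60,800 = 79.6%.

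The same number of missed days moves the ratio down or up according to where it falls. That is reweighting, not measurement of the gap.

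**Step 6: does the exposure table recover it?** SAP 7.5.1 summarises days on drug. A patient with 138 such days falls in the band "120 days <= duration of exposure <150 days" whether there were three 14-day gaps or a permanent stop on day 138. Lost days show there, but a gap cannot be told from an early stop.

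**The case against.** The strongest reply is that the CRF is not available. SAP 4.2.1 opens by saying that date, time, dose and frequency of administration are recorded, and the actual daily dose might be an average over all calendar days. In that case missed days would show: 42 of 180 days off gives 138/180 = 76.7%. This stands as a condition on the point. No document describes such averaging, and Protocol 6.8.3 describes dosages prescribed and dispensed and dose changes.

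A second reply is that sites check tablets and diaries at every visit, and Table 8-1 sends that assessment to the database. This is correct. It places the fault in the planned summary, not in data collection, and it offers a simple remedy.

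A third is that the consequence is small: a descriptive figure, a target addressed to investigators, and at least 36 of 180 days off drug before the target is missed. That also stands. The documents do not say how often such gaps occur.

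A reader might go further in four ways that the documents do not support:

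- *That missed days can never lower the ratio.* Step 5 shows that they can when a segment is taken below plan.
- *That the figure is too high for every patient with a gap.* Protocol 6.2.3 provides for temporary withdrawal of study drug in persistent hypotension. A gap ordered by the investigator is not non-compliance.
- *That the two periods are measured differently because one drug is taken once daily and the other twice.* The comparators in Protocol Table 6-2 include twice-daily and three-times-daily drugs, and how single missed doses are recorded is unknown.
- *That the efficacy result is affected.* The McNemar test does not use compliance, and SAP section 6 defines the per-protocol set by major protocol violations without reference to this ratio.

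**Conclusion.** The point holds in a limited form. As written, SAP 4.2.1 and 4.5 give a ratio of daily doses that does not measure whole missed days. A patient on full planned dose on dosing days scores 100% with 42 of 180 days off drug, when 76.7% of days were covered; across the visit windows the covered share runs from 72.4% to 79.8%. The compliance summary cannot show whether the protocol's target was met in the ACEI/ARB or the ARNI period.

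This rests on reading the actual daily dose as the dose on days taken, and on a 180-day period. The length matters little: at 182 days the target is first missed at 37 days off (145/182 = 79.7%). The effect is on interpretation of a descriptive summary. It should be corrected, but it does not threaten the primary analysis.

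**What to change.** Either of two changes to SAP 4.5 would do:

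1. For compliance only, compute total planned dose over all calendar days from first to last dose in the period, excluding interruptions ordered by the investigator, and count actual dose only on days with drug. Deleting the sentence that removes gaps would not be enough, because the two totals would still share one multiplier.
2. Summarise the tablet-count and diary compliance assessment that Table 8-1 schedules at Visits 2 to 7 for the clinical database.

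In both cases report n (%) above 80% by period beside the planned summary statistics. Keep the present duration of exposure for the table in SAP 7.5.1, and state in the SAP how the actual daily dose is recorded.

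The cost is one changed derivation and one added table row. First and last dose dates and off-drug days are already needed for the exposure calculation. Under the first option, ordered interruptions must be identifiable in the dosing records. Reported compliance may be lower.
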